7.1.3. Packaging and Labelling

The investigational products will be supplied by the sponsor or its designee in accordance with current Good Manufacturing Practices (cGMP).

Clinical trial materials will be labeled according to the country's regulatory requirements. All investigational products will be stored, inventoried, reconciled, and destroyed according to applicable regulations.

Ixekizumab and placebo to match will be supplied as an injectable solution in 1-mL, single-dose, prefilled, disposable manual syringes with study specific labels. Each syringe of ixekizumab is designed to deliver ixekizumab 80 mg. The syringes (and contents) containing either ixekizumab or placebo will be visibly indistinguishable from each other. Syringes will be supplied in cartons with the appropriate quantity of syringes specific to the planned dispensing schedule of the investigational product.

7.2. Method of Treatment Assignment

During the Lead-In Period (Period 1), patients who were previously receiving ixekizumab treatment during Studies RHBV and RHBW will, as of Week 0 in Study RHBY, continue to receive the same ixekizumab treatment regimen they were on at the end of the originating study, but now in open-label fashion.

For patients who were previously in Study RHBX, treatment during the Lead-In Period will be assigned as follows:

- Patients who were rescued to open-label ixekizumab 80 mg Q2W will remain on ixekizumab 80 mg Q2W in open-label fashion.
- Patients who were receiving blinded treatment with either ixekizumab 80 mg Q2W or ixekizumab 80 mg Q4W will continue on their ixekizumab dose regimen in blinded fashion.
- Patients who were receiving blinded treatment with placebo will be assigned to receive blinded treatment with ixekizumab 80 mg Q4W.

During the Extension Period (Period 2), patients in Group A who do not meet entry criteria for randomized withdrawal–retreatment will continue to receive the same ixekizumab dose regimen

that they were receiving during the Lead-In Period (ixekizumab 80 mg Q2W or ixekizumab 80 mg Q4W).

During the Extension Period (Period 2), patients in Group B, who have achieved a state of sustained remission, and meet the criteria for randomized withdrawal-retreatment (see Section 5.1), will be assigned to treatment groups as follows by a computer-generated random sequence using an interactive web-response system (IWRS).

- Patients in the ixekizumab 80 mg Q2W treatment group will be re-randomized to either ixekizumab 80 Q2W or placebo at 2:1 ratio allocation and will be stratified by region and originating study.
- Patients in the ixekizumab 80 mg Q4W treatment group will be re-randomized to either ixekizumab 80 mg Q4W or placebo at 2:1 ratio allocation and will be stratified by region and originating study.

During the Extension Period, the IWRS will be used to assign double-blind investigational product to each patient in Group B. Site personnel will confirm that they have located the correct investigational product package by entering a confirmation number found on the package into the IWRS.

7.2.1. Selection and Timing of Doses

Investigational product is to be administered at approximately the same time each day, as much as possible. For injections not administered on the scheduled day of the week from Week 0 to Week 104, the missed dose should be administered as soon as possible. Injection(s) for missed dose(s) should not be given within 5 days of the next scheduled dose; injections should be ≥5 days apart. Dates of subsequent study visits are not to be modified according to this delay.

A paper Study Drug Administration Log will be completed by patients for each injection throughout study participation. The data from the Study Drug Administration Log must be transcribed into the electronic case report form (eCRF) by site personnel.

Patients will be instructed to contact their study site in the event of an injection problem. In addition, site personnel will review all Study Drug Administration Logs at each visit to identify any product complaints, and they will complete a Product Complaint Form for each operation failure reported on a Study Drug Administration Log (see Section 9.2.3 for additional instructions regarding complaint handling).

7.3. Blinding

Patients, study site personnel, and study team in Study RHBY will remain blinded to the initial treatment assigned in the originating study (RHBV, RHBW, or RHBX) until the time of datalock for the respective originating study (i.e., Week 16 datalock for Studies RHBV and RHBW, and Week 52 datalock for Study RHBX).

During the Lead-In Period (Period 1), all patients from studies RHBV and RHBW will receive treatment with either ixekizumab 80 mg Q2W or ixekizumab 80 mg Q4W in open-label fashion. For patients from Study RHBX, patients who were rescued to open-label treatment with

ixekizumab 80 mg Q2W will continue to receive open-label treatment with ixekizumab 80 mg Q2W during the Lead-In Period. All other patients from Study RHBX will continue on blinded treatment in the extension Study RHBY until Week 52 datalock has occurred for Study RHBX.

During the Extension Period (Period 2), including blinded, randomized withdrawal-retreatment, patients who do not meet entry criteria for participation in the randomized withdrawal-retreatment period (Group A) will continue to receive ixekizumab 80 mg Q2W or ixekizumab 80 mg Q4W. Patients having achieved a state of sustained remission and do meet the criteria outlined in Section 5.1 (Group B) will participate in the double-blind, placebo-controlled, randomized withdrawal-retreatment period. During the randomized withdrawal-retreatment period, patients in Group B, study site personnel, and study team will be blinded to study treatment randomization. Patients participating in the randomized withdrawal-retreatment period will continue to receive blinded treatment until the completion of the study or time of flare. Upon flare, patients will be retreated with the ixekizumab treatment regimen assigned in Period 1 in an open-label fashion. Patients who experience a flare and were originally from Study RHBX will not receive open-label treatment until the Week 52 datalock has occurred for Study RHBX.

During the Long-Term Extension Period (Period 3), patients from Group A will continue to receive ixekizumab 80 mg Q2W or ixekizumab 80 mg Q4W. Patients from Group B will continue the same treatment they were receiving at the end of Period 2 (ixekizumab 80 mg Q2W, ixekizumab 80 mg Q4W, or placebo) in blinded fashion until the completion of the study or time of flare. Upon flare, patients will be retreated with the ixekizumab treatment regimen assigned in Period 1 in an open-label fashion. As of Week 64, patients initially treated with ixekizumab 80 mg Q4W during Period 1 may have their dose escalated to ixekizumab 80 mg Q2W, in an open-label fashion, only after the patient has experienced a flare and been subsequently retreated with ixekizumab 80 mg Q4W for at least 12 weeks.

Patients who experience a flare and were originally from Study RHBX will not receive open-label treatment until the Week 52 datalock has occurred for Study RHBX.

Emergency unblinding for AEs may be performed through the IWRS, which may supplement or take the place of emergency codes generated by a computer drug-labeling system. This option may be used ONLY if the patient's well-being requires knowledge of the patient's treatment assignment. All actions resulting in an unblinding event are recorded and reported by the IWRS.

If an investigator, site personnel performing assessments, or a patient is unblinded, the patient is to be discontinued from study treatment. In cases where there are ethical reasons to have the patient remain on study treatment, the investigator must obtain specific approval from a Lilly clinical research physician or Lilly clinical research scientist for the patient to continue on study treatment.

In case of an emergency, the investigator has the sole responsibility for determining if unblinding of a patient's treatment assignment is warranted. Patient safety must always be the first consideration in making such a determination. If the investigator decides that unblinding is warranted, the investigator is requested to make every effort to contact the Lilly clinical research

physician/clinical research scientist prior to unblinding a patient's treatment assignment unless this could delay emergency treatment of the patient. If the patient's treatment assignment is unblinded, Lilly must be notified immediately.

7.4. Dosage Modification

As described in Section 5.1, if a patient who has achieved a state of sustained remission (Group B) during the randomized withdrawal-retreatment period experiences a flare and meets the criteria for retreatment, the patient will be retreated with the ixekizumab treatment regimen that he or she was receiving prior to withdrawal (ixekizumab 80 mg Q2W or ixekizumab 80 mg Q4W). During Period 2, retreatment will begin at the next scheduled visit. During Period 3, given the longer interval between visits, retreatment may begin at the next scheduled visit or at an unscheduled visit prior to the next scheduled visit.

As of Week 64, patients in Group A receiving ixekizumab 80 mg Q4W may have their dose escalated to ixekizumab 80 mg Q2W in Period 3 if the investigator determines that the patient may benefit from an increase in frequency of dosing to achieve adequate disease control. Dose escalation may begin at the next scheduled visit or at an unscheduled visit prior to the next scheduled visit.

As of Week 64, patients in Group B ([Table RHBY.3](#)):

- who are receiving placebo will remain on placebo, and will be monitored per the Schedule of Activities (Section 2) for eligibility (i.e., flare) to be retreated with the ixekizumab treatment regimen they were receiving prior to withdrawal (ixekizumab 80 mg Q2W or ixekizumab 80 mg Q4W).
- who are receiving ixekizumab 80 mg Q4W may have their dose escalated to ixekizumab 80 mg Q2W in Period 3 if the investigator determines that the patient may benefit from an increase in dosing to achieve adequate disease control. Escalation to ixekizumab 80 mg Q2W may occur only after the patient has been retreated upon flare with the ixekizumab treatment regimen received during Period 1 (ixekizumab 80 mg Q4W) for at least 12 weeks.
- who are receiving ixekizumab 80 mg Q2W will remain on this dose until completion of the study or early discontinuation.

Table RHY.3. Dosage Modification for Group B during Period 2 and Period 3

Period 1 (Open-Label)	Period 2 (Blinded)	Period 3 (Blinded)	If Flare during Period 2 or 3, Retreat (Open-Label)	12 Weeks after Retreat, Escalate (Period 3) (Open-Label)
ixekizumab 80 mg Q2W	ixekizumab 80 mg Q2W	ixekizumab 80 mg Q2W	ixekizumab 80 mg Q2W	N/A
	placebo	placebo	ixekizumab 80 mg Q2W	N/A
ixekizumab 80 mg Q4W	ixekizumab 80 mg Q4W	ixekizumab 80 mg Q4W	ixekizumab 80 mg Q4W	ixekizumab 80 mg Q2W
	placebo	placebo	ixekizumab 80 mg Q4W	ixekizumab 80 mg Q2W

Abbreviations: N/A = not applicable; Q2W = every 2 weeks; Q4W = every 4 weeks.

Note: Patients from Group B who experience a flare and meet criteria for retreatment during Period 2 or Period 3 will be retreated with the ixekizumab treatment regimen received during Period 1 in an open-label fashion. As of Week 64, patients initially treated with ixekizumab 80 mg Q4W during Period 1 may have their dose escalated to ixekizumab 80 mg Q2W, in an open-label fashion, only after the patient has experienced a flare and been subsequently retreated with ixekizumab 80 mg Q4W for at least 12 weeks. Patients who experience a flare and were originally from Study RHBX will not receive open-label treatment until the Week 52 datalock has occurred for Study RHBX.

In addition, Section 9.4.10.1 describes instances where drug may be withheld.

Other than these exceptions, investigational product dose modifications are not permitted.

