
Abbreviations: cDMARD = conventional disease modifying antirheumatic drug; COX-2 = cyclooxygenase-2; eCRF = electronic case report form; MTX = methotrexate; NSAID = nonsteroidal anti-inflammatory drug; SJC = swollen joint count; TJC = tender joint count.

Other Concomitant Medications:

Patients requiring surgery at any time during the study are to interrupt administration of the investigational product beginning 8 weeks prior to the surgery, or as early as possible within 8 weeks of surgery, and resume administration of the investigational product only after complete wound healing.

If the need for concomitant medication arises, the investigator is to base decisions on the patient and on clinical factors. Any additional medication, whether prescription or over-the-counter, used at baseline and/or during the course of the study, must be documented with the start and stop dates in the eCRF. Additional systemic drugs are to be avoided during the study, unless required to treat an AE. Other medications may be allowed, if approved by the sponsor or its designee.

Only for patients who discontinued study treatment and have entered the Post-Treatment Follow-up Period, axSpA therapy with another agent previously excluded during the treatment period of the study may be allowed, as determined appropriate by the investigator and approved by Lilly medical.

Any changes in medications not addressed above are to be discussed with the investigator. Patients must be instructed to consult the investigator or other appropriate study personnel at the site before taking any new medications or supplements.

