[13] The patient becomes hepatitis B virus (HBV) deoxyribonucleic acid (DNA) positive. The patient is to be referred to a specialist physician. Discussion of the timing of discontinuation from study treatment and from the study is provided in Section [9.4.10.2](#).

8.1.2. *Temporary Discontinuation from Study Treatment*

Section [9.4.10.1](#) describes instances where drug may be withheld.

8.1.3. *Discontinuation of Inadvertently Enrolled Patients*

The criteria for enrollment must be followed explicitly. If the sponsor or investigator identifies a patient who did not meet enrollment criteria and was inadvertently enrolled, a discussion must occur between the sponsor clinical research physician and the investigator to determine if the patient may continue in the study. If both agree it is medically appropriate to continue, the investigator must obtain documented approval from the sponsor clinical research physician to allow the inadvertently enrolled patient to continue in the study with or without treatment with investigational product.

8.2. *Discontinuation from the Study*

Some possible reasons that may lead to permanent discontinuation include:

- enrollment in any other clinical trial involving an investigational product or enrollment in any other type of medical research judged not to be scientifically or medically compatible with this study.
- participation in the study needs to be stopped for medical, safety, regulatory, or other reasons consistent with applicable laws, regulations, and GCP.
- patient decision: the patient requests to be withdrawn from the study.

Patients who discontinue the study participation early will have end-of-study procedures performed as shown in the Schedule of Activities (Section 2).

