9.4.6. Tuberculosis Testing

Tuberculosis testing will be conducted based on clinical assessment of TB risk (symptoms/signs/known or suspected TB exposure), and as required by local regulations and/or local standard of care.

Patients with a positive TB test and/or other evidence of active TB should be discontinued (Section 8.1.1).

In patients with a positive TB test indicating TB test conversion since prior testing (based on patient medical history), but no other evidence of active TB, study treatment should be withheld. These patients may continue in Study RHBY and resume study treatment without repeating TB testing if all of the following conditions are met:

- a specialist in the care of patients with TB (e.g., infectious disease or pulmonary medicine subspecialists) is consulted and does not identify evidence of active TB, and the patient is assessed as having latent TB infection
- a posterior-anterior view chest x-ray or results from a chest x-ray obtained within 30 days prior to the positive TB test does not indicate active TB infection
- after receiving at least the initial 4 weeks of appropriate latent TB infection (LTBI) therapy with no evidence of hepatotoxicity (ALT/AST must remain $\leq 2 \times \text{ULN}$) upon retesting of serum ALT/AST
- meet all other inclusion/exclusion criteria for participation

Such patients must complete appropriate LTBI therapy in order to remain in compliance and continue to participate in the study.

If a positive TB test result is believed to represent a false-positive result based on thorough medical assessment of the patient, the investigator should discuss further testing and management with Lilly medical.

Any findings of a positive TB test that occurs after the patient receives the first dose of study treatment are to be reported to Lilly or its designee as an AE via CRF.

9.4.7. *Quick Inventory of Depressive Symptomatology—Self-Report (16 Items)*

For each patient, a QIDS-SR16 assessment will be collected according to the Schedule of Activities (Section 2).

Any clinically significant findings from the QIDS-SR16 assessment that result in a diagnosis and that occur after the patient receives the first dose of study treatment are to be reported to Lilly or its designee as an AE via CRF.

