9.4.10.3. Hypertension

Patients who experience changes in BP (systolic BP at ≥160 mm Hg plus ≥20 mm Hg increase from baseline [Week 0; Visit 1]; and/or diastolic BP at ≥100 mm Hg plus ≥10 mm Hg increase from baseline) on 2 consecutive visits are to receive intervention for the management of hypertension. Intervention could include the maximal intervention of withholding the dose of investigational product and/or the introduction of antihypertensive agent(s) as medically appropriate.

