## 6.8. Treatment Compliance

Throughout treatment periods, patients will record information in a Study Drug Administration Log (captured in the *Exposure as Collected* eCRF page), including the date, time, and anatomical location of administration of investigational product, syringe number, who administered the investigational product, and the reason if the investigational product is not fully administered.

Treatment compliance for each patient per period will be calculated as:

$$\text{Treatment compliance (\%)} = 100 \times \frac{\text{Total number of injections administered}}{\text{Total number of injections prescribed}}$$

- The total number of injections prescribed varies by period and can be derived from the IWRS study drug dispense dataset.
- The total number of injections administered will be derived using the response to the question "Was dose administered?" on the *Exposure as Collected* eCRF page.

A patient will be considered overall compliant with study treatment within each treatment period if he/she misses no more than 20% of the expected doses, does not miss 2 consecutive doses, and does not over-dose (ie, take more injections at the same time point than specified in the protocol).

Patient treatment compliance by treatment week and overall will be summarized for the following periods and populations:

- Combined Periods 1 and 2 (Lead-In Period Safety Population)
- Combined Periods 1, 2, and 3 (Lead-In Period Safety Population)
- Period 2 (RW Safety Population) by treatment group
- Period 3 (RW Safety Population) by treatment group

The comparisons between treatment groups for RW Safety Population during Period 2 will be conducted using Fisher's exact test.

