Important Protocol Deviation Category/Subcategory/Study Specific	Source to Identify Protocol Deviation a	Statistical Programming Guidance for Clinical Study Report
Category: Investigational Product		
Subcategory: Treatment Assignment/Randomization Error		
Took incorrect study medication	Stats and monitor	If IWRS study drug dispense data not match with the treatment label identifier on the Exposure as Collected eCRF page From monitor's list: Randomized patients should consistently take the assigned medication during Period 2
Not meet sustained remission at randomization, but randomized in Group B	Stats	Stats will program based on ASDAS score using remission criteria: ASDAS <1.3 at Week 16 and Week 20, or ASDAS <1.3 at Week 16 or Week 20, and ASDAS <2.1 at the other visit.
Subcategory: Compliance	Stats	If non-compliant with study medication regimen or over-dose during the treatment period. Note: Non-compliance with therapy is defined to be missing more than 20% of expected doses or missing 2 or more consecutive doses; over-dose is defined as to take more injections at the same time point than specified in the protocol. Note: For non-compliance programming, Week 64 is included in Period 3 not Period 2.
Subcategory: Patient took medication not fit for use	Monitor	From monitor's list
Subcategory: Other		
Randomized but did not take any study medication	Stats	If a patient is randomized but does not take any study medication
Category: Safety		
Subcategory: SAEs		
Not reported in 24 hours	Monitor	From monitor's list
Category: Informed Consent		
Subcategory: Informed Consent not Obtained		
Procedure done prior to or without consent	Monitor and Stats	Either from monitor's list, or, If patient informed consent date is after Visit 1 date or missing informed consent

Important Protocol Deviation Category/Subcategory/Study Specific	Source to Identify Protocol Deviation a	Statistical Programming Guidance for Clinical Study Report
Category: administrative/oversight		
Subcategory: Regulatory/Ethic Approvals	Monitor	From monitor's list
Subcategory: Other	Monitor	From monitor's list
Enrolled in a site with significant GCP non-compliance issue	Monitor	From monitor's list

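### Protocol 7.4 and 8.1.2 recognise only neutropenia holds although other sections direct or allow more, and the compliance rule has no exemption for such holds

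*Protocol*

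**What the plan says.** **Grounds for a hold.** Protocol 7.4 describes retreatment after flare and escalation from Week 64. It then adds: "In addition, Section 9.4.10.1 describes instances where drug may be withheld". Its last sentence is: "Other than these exceptions, investigational product dose modifications are not permitted". Section 9.4.10.1 is the neutropenia section. Section 8.1.2, the only section on temporary discontinuation, is a single sentence saying that the same section "describes instances where drug may be withheld".

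Other sections provide for further holds:
- 7.7 (surgery, directed): patients are to "interrupt administration of the investigational product beginning 8 weeks prior to the surgery", or as soon as possible inside that window, and resume only once the wound has healed.
- 9.4.6 (TB test conversion, directed): where there is conversion "but no other evidence of active TB, study treatment should be withheld"; resumption requires at least 4 weeks of latent-TB therapy.
- 8.1.1, note to criterion 2 (laboratory retest, directed): no dosing until the retest result is known.
- 9.4.10.3 (hypertension, allowed): the options include the "maximal intervention of withholding the dose of investigational product", with no length given.

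**Scoring of missed doses.** Protocol 10.3.2.4 defines compliance per study period. SAP 6.8 repeats the rule: a patient is compliant who "misses no more than 20% of the expected doses, does not miss 2 consecutive doses" and does not overdose. SAP Table RHBY.6.11 turns the converse into an important protocol deviation: "Non-compliance with therapy is defined to be missing more than 20% of expected doses or missing 2 or more consecutive doses". None of the three exempts a dose withheld because the protocol directs or allows it. SAP 6.8 says that the reason is recorded when product is not fully administered, but the rule does not use it.

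**The concern.** There are two linked problems.

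First, the general rule in 7.4 and the specific rules elsewhere cannot both be followed as written. A site that holds drug for surgery or a TB conversion obeys 7.7 or 9.4.6 and breaches the closing sentence of 7.4. A site that obeys 7.4 breaches the specific section.

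Second, a site that follows a directed hold can produce a patient who is scored as non-compliant and listed with an important protocol deviation, which SAP 6.15 defines as a violation of the protocol. That mixes protocol-directed interruption with true non-adherence in the compliance summaries, in the Fisher comparison of compliance between arms in Period 2, and in the deviation table.

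**Working it through.** No stated figure needs reproducing. The check is a comparison of passages and a dose count.

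**Do the passages conflict?** It could be said that a hold is not a dose modification, so the bar in 7.4 does not touch it. But 7.4 places the 9.4.10.1 holds among its own exceptions, so it treats withholding as something that needs one. Neither 7.4 nor 8.1.2 cross-refers to 7.7, 9.4.6, the 8.1.1 note or 9.4.10.3. The conflict is real.

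**Does a hold trip the compliance rule?**

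Inputs:
- Period lengths: 24 weeks (Period 1), 40 weeks (Period 2), 40 weeks (Period 3), from Protocol 5.1.
- Injection interval: 2 weeks on Q2W, and on blinded Q4W where Table RHBY.2 alternates active and placebo injections; 4 weeks on open-label Q4W.
- Hold lengths: 8 weeks for a full pre-surgery hold; 4 weeks as the minimum TB hold; up to 8 weeks for a neutropenia hold running through two repeat tests, each due within 4 weeks.

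Formulas:
- Expected injections = period length / interval. Period 1: 24/2 = 12 or 24/4 = 6. Periods 2 and 3: 40/2 = 20 or 40/4 = 10.
- Consecutive injections missed = hold length / interval.
- Flagged if 2 or more consecutive are missed, or missed/expected exceeds 20%.

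Results for a hold lying inside one period:

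| Hold | Interval | Missed | Period 1 | Period 2 or 3 | Flagged |
|---|---|---|---|---|---|
| Surgery, full 8 weeks | 2 weeks | 8/2 = 4 | 4/12 = 33.3% | 4/20 = 20.0% | yes |
| Surgery, full 8 weeks | 4 weeks | 8/4 = 2 | 2/6 = 33.3% | 2/10 = 20.0% | yes |
| TB, minimum 4 weeks | 2 weeks | 4/2 = 2 | 2/12 = 16.7% | 2/20 = 10.0% | yes |
| TB, minimum 4 weeks | 4 weeks | 4/4 = 1 | 1/6 = 16.7% | 1/10 = 10.0% | no |
| Neutropenia, two repeats | 2 weeks | up to 8/2 = 4 | up to 33.3% | up to 20.0% | yes, at that length |

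In Periods 2 and 3 a full surgery hold is exactly 20%, which is not more than 20%; the consecutive-dose limb does the flagging. The hypertension hold has no stated length: 1 missed dose is compliant, 2 or more consecutive are not. The same holds for the retest pause.

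**Where the rule does not bite.** Compliance is judged per period, so a hold across a boundary can escape. An 8-week hold on open-label Q4W split one dose to each side leaves 1 missed in each period, and both are compliant. A surgery hold started late can also be shorter than 8 weeks.

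**The case against.** The strongest reply has four parts.

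1. *The specific instruction governs.* The surgery, TB and blood-pressure instructions are explicit and sit where a site would look, and 8.1.2 is worded as a pointer, not an exclusive list. This is fair for 8.1.2. It does not rescue 7.4, whose last sentence is categorical.

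2. *The primary analysis is not touched.* A reader might infer that sites, seeing no permitted hold, would stop drug permanently, and that nonresponder imputation would then count these patients as flares. The documents do not support that chain. Surgery and hypertension are not among the permanent-discontinuation criteria in 8.1.1. Section 9.4.6 has a broadly worded sentence on discontinuing after a positive TB test, but it refers to 8.1.1, whose criterion 4 stops a converter only if latent TB goes without appropriate treatment or there is active disease. Nonresponder imputation applies to discontinuation of study treatment, and nothing equates a hold with that. No analysis population excludes patients for non-compliance or a deviation. This part stands.

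3. *Not every hold is flagged.* It is tempting to say that every directed hold is scored as a violation. That is too strong: the outcome depends on the doses missed, and the working shows several holds that stay compliant. This part stands too.

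4. *The count of expected doses is open.* Neither document defines the term. SAP 6.8 takes injections prescribed from the IWRS dispensing data, and Table RHBY.6.11 leaves detailed programming to a separate specification. A programmer could leave withheld doses out. That is possible, but the text does not say so, and a rule that can be programmed either way needs the same correction. The recorded reasons and the by-patient deviation listing would help a reader separate the cases by hand, but the planned summaries and test would not.

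**Conclusion.** The point holds in two parts. Protocol 7.4, with 8.1.2, contradicts 7.7, 9.4.6, the 8.1.1 note and 9.4.10.3 on when drug may be withheld, and the passages must be reconciled. The compliance rule, which originates in Protocol 10.3.2.4 and is repeated in SAP 6.8, has no exemption for holds that the protocol directs or allows; Table RHBY.6.11 adds the status of important deviation. It applies equally to neutropenia holds, which 7.4 does recognise.

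As written, any hold costing 2 or more consecutive doses in a period is flagged. That covers a full 8-week surgery hold within one period on either interval, a 4-week TB hold within one period on 2-weekly injections, and a neutropenia hold that runs through both repeats.

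This rests on three assumptions: withheld doses count as expected, placebo injections count as doses, and the dose at a period's end belongs to the next period (Table RHBY.6.11 says so for Week 64). The documents give no frequency for these holds, so the number of patients affected cannot be estimated.

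The effect is confined to the compliance summaries, the Period 2 comparison of compliance and the important-deviation table. No effect on the primary analysis is shown. The point is worth correcting because the rule gives a misleading result and the correction is cheap.

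**What to change.** - **Protocol.** Reconcile 7.4 and 8.1.2 with 7.7, 8.1.1, 9.4.6, 9.4.10.1 and 9.4.10.3, so that one list names every circumstance in which the protocol directs or allows a hold. This is cross-referencing only; it changes no clinical rule.
- **Compliance rule.** In Protocol 10.3.2.4, SAP 6.8 and SAP Table RHBY.6.11 together, define expected doses so that doses withheld under those sections leave both the percentage and the consecutive-missed count. Changing the SAP alone would leave it at odds with the protocol's own definition.
- **Reporting.** Show these doses separately as protocol-directed interruptions.

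The cost is clarifying wording in the protocol and one programming rule in the SAP. No new data are needed, provided that the reason for non-administration which SAP 6.8 says is collected is specific enough to identify a directed or allowed hold; that should be checked against the case report form.
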